5.1.2 Part B - Optional Open-label Extension

The following procedures and study visits are optional for participants who successfully complete Part A. The study design schematic for Part B is presented in Figure 5.1.2-1.

Figure 5.1.2-1: Study Design Schema (Part B)

Abbreviations: [REDACTED]; PK, pharmacokinetics; QD, once daily; TTE, transthoracic echocardiogram.

Note: Phone visits will be conducted every [REDACTED] beginning at [REDACTED]. Clinic visits will be conducted every [REDACTED] beginning at [REDACTED]. All visits have a [REDACTED] day window. See Table 2-3.

a [REDACTED].

b Biomarker samples will be collected at Screening B (if applicable), Day [REDACTED].

c Screening visit as needed. See Section 5.1.2.1.

5.1.2.1 Screening Period (Part B)

Screening for Part B will be conducted at EOS-A **or** a separate Screening Visit as follows:

- 1) **EOS-A Visit as Screening Visit for Part B:** The assessments taken at the EOS-A visit may be used in place of the Screening visit for Part B as long as the informed consent for Part B is signed and the Day 1B visit occurs within [REDACTED] of EOS-A.

- 2) **Separate Screening Visit for Part B:** Participants for whom the Day 1B visit will occur more than [REDACTED] past EOS-A will require a separate screening visit for Part B. The screening visit will be conducted after participants provide signed informed consent for Part B. Participants will undergo a variety of general and laboratory assessments to assess eligibility (see [Table 2-5](#)). Screening tests include, but are not limited to, 12-lead ECGs, assessment of [REDACTED], and TTE at rest, with Valsalva Maneuver, and post-exercise.

5.1.2.2 Treatment Period (Part B)

All participants will receive MYK-224. Dosing will consist of a QD oral dose in the form of tablets. Treatment will begin on Day 1B with each participant receiving either the dose at which they completed Part A or a dose of 5 mg if there have been certain modifications in a participant's background HCM therapy following completion of Part A (see [Section 7.4.2](#) and [Table 7.4.2-1](#) for details).

- Every effort should be made to continue all participants on the background therapy on which they completed the first part of the study.
- Participants that have had no change in background HCM therapy or those that have had a discontinuation of background therapy, or a decrease in the dose of background therapy, will start at the MYK-224 dose on which they completed Part A.
- Participants that completed Part A at a dose of 5 mg MYK-224 or higher and have begun a new permitted background HCM therapy (see [Section 6.2](#) criteria 3) f) and 3) g)) or have had a dose increase in background HCM therapy may either:
 - Resume their prior HCM therapy with at least a [REDACTED] washout period prior to the screening visit for Part B (preferred) **or**
 - Continue current background HCM therapy (no dose adjustments within [REDACTED] of screening) and start Part B on a 5-mg dose of MYK-224.
- Participants who completed Part A at a dose of 2.5 mg of MYK-224 and have a subsequent dose increase in HCM therapy or new permitted HCM therapy must either resume prior background HCM therapy or discontinue new therapy prior to starting Part B at a 2.5-mg dose.
- Participants who have begun a background HCM therapy that is not permitted in Part B (see [Section 6](#) [Study Population]) will need to discontinue these therapies for at least [REDACTED] prior to the Part B Screening visit to participate in the OLE part of the study.

Dose modification of MYK-224 is permitted (see [Section 7.4.2](#) for details) and will be guided by site-read TTEs. Study investigators will not be blinded to the TTE results from these visits. Echocardiograms will also be sent to a core laboratory for future data analysis. Participants will continue QD dosing of MYK-224 at home, with the exception of clinic visit days, where the daily dose will be given at the clinic in order to collect predose samples. Where possible, participants should remain on the background HCM therapy on which they initiated the OLE part of the study (Part B). After [REDACTED] background therapy may be decreased or discontinued in consultation and agreement with the Medical Monitor.

Participants will return to the investigational site at [REDACTED] until EOT-B, as outlined in [Table 2-5](#) and [Table 2-6](#). These clinic visits will include PK sample collection, [REDACTED], safety laboratory collection, 12-lead ECGs, clinical evaluations (eg, vital signs, COAs, concomitant medication use), and echocardiography.

Telephone visits will be conducted starting at [REDACTED] thereafter ([REDACTED]) to assess for AEs, concomitant medication use, and results of any monthly at-home pregnancy tests that may occur outside of scheduled clinic visits, as outlined in [Table 2-5](#).

The final dose of MYK-224 will be administered in the clinic at the EOT-B visit ([REDACTED]).

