5.1.1.3 Washout and End of Study (Part A)

[figure not shown]
All participants will have a [REDACTED] washout period following the final dose of MYK-224. Participants will have a clinic visit at the second week (at least [REDACTED] after the last dose of MYK-224) of washout and an EOS-A clinic visit after the washout period is complete (at least [REDACTED] after the final dose of MYK-224). Refer to Table 2-4 for a list of assessments performed at these clinic visits.

An example dose titration schematic is presented in [REDACTED]

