The objective of the study is to evaluate the safety, tolerability, and efficacy of MYK-224 alone and in combination with SOC therapies for HCM. The cohorts are staggered so that data from ongoing studies may be evaluated prior to initiating Cohort 2 to allow for modification of the starting dose or dose titration schedule if necessary. Cohort 2 includes participants with SOC consisting of either a nondihydropyrimidine calcium channel-blocker (verapamil or diltiazem) or dihydropyrimidine in combination with a beta-blocker or nondihydropyrimidine calcium channel-blocker. Both verapamil and diltiazem are moderate inhibitors of CYP3A4.

The initiation of Cohort 2 will be at the discretion of the Sponsor and will be informed by data obtained from Cohort 1, as well as from 2 on-going studies: 1) CV029005, a DDI study evaluating the effect of co-administration of MYK-224 and moderate (verapamil) and strong (itraconazole) [REDACTED] in healthy participants; 2) MYK-461-017 (VALOR-HCM), a clinical study evaluating mavacamten (a similar cardiac myosin inhibitor) in participants with oHCM who are eligible for septal reduction therapy, which includes the [REDACTED]. Cohort 2 will only be initiated once 50% of Cohort 1 participants have reached their target dose and the data from the CV029005 and VALOR-HCM study are available. The same dosing regimen as Cohort 1 will be used for Cohort 2 unless data from Cohort 1 and the indicated studies supports a change to this schedule.

Participants who successfully complete Part A will have the option to continue the study drug as a participant in Part B, a 2-year OLE study. In Part B, participants will start at the dose of MYK-224 on which they completed Part A with the exception of those who have had a change in background HCM therapy. In instances where participants have had adjustments in background HCM therapy following their completion of Part A, they may either resume the background therapy upon which they completed Part A at least [REDACTED] prior to screening for Part B or start Part B at a 5-mg dose (see [Section 7.4](#)). After the initial [REDACTED] of Part B, clinic visits will occur every [REDACTED] and will include clinical evaluation of symptoms, AE/SAE assessment, ECGs, TTEs, PK sampling, [REDACTED], and laboratory assessments. Dose modifications during Part B will be guided by local site-read TTEs (See [Section 7.4.2](#) for details).

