5.5 Justification for Dose

The current study design in Part A allows for a measured and stepwise exploration of doses, with the maximum dose for each participant limited by a normalization of cardiac contractility or resolution of clinical parameters of LVOT obstruction.

In a previous study with a similar compound (mavacamten), the exposure-response relationship for LVEF varied between healthy volunteers (HV) and HCM patients, with a higher baseline LVEF and a steeper slope for HCM patients. These observations are likely a manifestation of the underlying pathobiology of sarcomeric hypercontractility that is a hallmark of the disease. We anticipate a similar phenomenon with MYK-224 and have thus chosen a starting dose and an echocardiography-based dose titration scheme that will allow for safe and stepwise dose modification guided by each participant's response parameters.

[REDACTED]. Additionally, given that HCM patients may exhibit relief of LVOT obstruction at lower exposures than at which effects on LVEF are observed, participants that demonstrate a clinical response at [REDACTED]

The starting dose of MYK-224 in the current study will be 5 mg, which has been shown to be safe and well-tolerated in the FIH study in normal healthy participants.

[REDACTED]

[REDACTED]

Participants will resume dosing in Part B at the dose they had completed Part A. This serves as a reasonable starting point for further dosing since this is a dose that was selected according to each participant's echocardiographic response to the study drug and was a dose that was tolerated to study completion. In cases where background therapy was modified between study parts, participants will either resume previous therapy prior to screening and start at the dose they completed in Part A or start at a 5-mg dose (see [Section 7.4](#) for details on starting dose for Part B). This will allow a safe starting point for subsequent dose titration to identify a new dose in the context of altered background therapy.

[REDACTED] (see [Section 7.4](#) [Dose Modification]). The dose of MYK-224 may be decreased at any time during the study based on

the clinical judgement of the investigator in discussion with the Medical Monitor. [REDACTED]
[REDACTED] (see [Section 8.1](#)).

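### Part B's no-adjustment interval for continued background HCM therapy is tied to Screening, which may be EOS-A, so it does not ensure a stable regimen before Day 1B (minor)

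*Combined protocol and SAP*

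**What the plan says.** Section 5.1.2.2 gives two options to participants who completed Part A at 5 mg or more and then began, or increased the dose of, a permitted background HCM therapy.

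- **Resume** the earlier therapy, with a "washout period prior to the screening visit for Part B (preferred" option). Sections 5.4 and 5.5 repeat this: "they may either resume the background therapy upon which they completed Part A at least" a redacted time before Part B screening, and "participants will either resume previous therapy prior to screening and start at the dose they completed in Part A".
- **Continue** the new regimen and start MYK-224 at 5 mg: "Continue current background HCM therapy (no dose adjustments within" a redacted interval of screening).

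Section 5.1.2.1 defines which visit counts as screening. "The assessments taken at the EOS-A visit may be used in place of the Screening visit for Part B", provided Part B consent is signed and Day 1B falls within a redacted time of EOS-A. A separate visit is mandatory in one visible case: "Participants for whom the Day 1B visit will occur more than" that time after EOS-A. Section 6.1 (Part B) gives a 28-day screening window. The footnote to the Part B schema says "Screening visit as needed" and refers back to 5.1.2.1. No visible sentence makes a change in background therapy a reason for a separate visit.

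Section 7.7.1 asks for background dosing to be held through the EOS visit in Part A, and it foresees adjustments between Parts A and B.

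**The concern.** The interval exists so that MYK-224 is restarted on a settled background regimen. Under 7.7.1 a compliant change comes after EOS-A. If EOS-A is also Part B Screening, the interval is anchored to a date before the change that it is meant to control.

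Table 3.3.1-1 says that other negative inotropic agents may add to the risk of systolic dysfunction. It lists as a mitigation a minimum level of LV systolic function, required while background therapy is at stable doses. On this route the screening echo comes from the "EOS-A clinic visit after the washout period is complete", and so before the new or increased drug. It cannot show LVEF on the regimen in use at Day 1B.

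**Working it through.** The plan states no figure here, so there is none to reproduce. The check is one of visit order, with days counted under stated assumptions.

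**Inputs**
- EOS-A = day 0 = Part B Screening.
- D = day of Day 1B. Taken as 28, from the 6.1 window; the limit in 5.1.2.1 is redacted. D = 21 and D = 14 are also tried.
- W = the redacted no-adjustment interval. Assumed to be 14 days, as in Part A exclusions 3)f) and 3)g); range 7 to 28.
- c = day on which permitted therapy is started or increased, 1 to D.

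**Rules**
- Time on the regimen at Day 1B = D − c. It is short if D − c < W, that is, if c > D − W.
- Backward reading: only changes before EOS-A count, so every c is admitted. Short and admitted: c > D − W.
- Two-sided reading: c ≤ W is barred. Short and admitted: c > max(W, D − W). Stable but barred: c ≤ min(W, D − W).
- Day 1B anchor: c is admitted only if c ≤ D − W, so none is short.

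**Results for D = 28 (number of change days, with the days in brackets)**

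| W | Backward: short, admitted | Two-sided: short, admitted | Two-sided: stable, barred | Day 1B anchor: short, admitted |
|---|---|---|---|---|
| 7 | 7 (22–28) | 7 (22–28) | 7 (1–7) | 0 |
| 14 | 14 (15–28) | 14 (15–28) | 14 (1–14) | 0 |
| 21 | 21 (8–28) | 7 (22–28) | 7 (1–7) | 0 |
| 28 | 28 (1–28) | 0 | 0 | 0 |

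At W = 14 the two-sided reading works the wrong way round. It bars days 1–14, which leave 27 down to 14 days on the regimen at Day 1B. It admits days 15–28, which leave 13 down to 0.

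**Sensitivity to D at W = 14**
- D = 21: two-sided c > max(14, 7) = 14, so days 15–21 (7). Backward c > 7, so days 8–21 (14).
- D = 14: two-sided c > 14, so none (0). Backward c > 0, so days 1–14 (14).

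These counts include a change on Day 1B itself; leaving that day out lowers each non-zero short-and-admitted count by one. They are possible change days, not frequencies.

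**The case against.** **The wording can be read more kindly.** A therapy that is current and unadjusted around screening is most naturally one already in place at screening. A drug started after EOS-A would then need a separate visit. If sites read it so, the gap closes, but they have to infer it: 5.1.2.2 is about changes made after Part A, and 5.1.2.1 names only elapsed time.

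**The result depends on redacted text.** On the two-sided reading the count is 0 at W = 28, and also at W = 14 with Day 1B on day 14. The starting-dose table, exclusions 9)c) and 9)d), and parts of Table 2-5 are redacted and may hold a rule. This stands and limits confidence.

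**Safeguards exist.**
- The start is at 5 mg, and 7.4.2 lets the investigator go lower.
- Sections 7.4.2 and 9.1.1.2, with the procedure order under Table 2-5, point to a resting echo before dosing on Day 1B.
- Eligibility criteria are reviewed again on Day 1.
- Section 7.7 asks for Medical Monitor agreement before any concomitant medication is given.
- Section 7.4.2 asks for a safety visit after a background therapy adjustment, though whether this reaches changes before Day 1B is arguable.

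These reduce the risk, but none visibly sets a stable interval. The Day 1B echo is also not clearly the entry value: criterion 6)c) names the Screening visit, and 6.4.1 uses the latest result before the first day of treatment.

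**Part A also anchors to Screening.** True, but Part A covers the time afterwards: 3)f) and 3)g) exclude an anticipated change of regimen for the listed drugs, and 7.7.1 asks for dosing to be maintained. Visible Part B text asks for every effort to keep therapy unchanged, yet expressly allows a changed regimen to continue.

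**A stronger reading that fails.** A reader might infer that the resume option is broken too, because a washout before EOS-A cannot follow a change made after it. The documents do not support that. Use of EOS-A is permissive, so the washout can be met through a separate Screening B visit. The wording in effect requires one, although it does not say so.

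**Conclusion.** The point holds as a minor one, for the continue option only. It concerns participants who finished Part A at 5 mg or more, whose permitted therapy was started or increased after EOS-A, and whose EOS-A assessments serve as Part B Screening. For them the condition can be satisfied with little or no stable time before Day 1B. That is certain on the backward reading. On the two-sided reading it depends on the redacted length and on when Day 1B falls.

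The number affected is not stated and is probably small. The visible primary and secondary endpoints concern Part A, so those results are untouched. A reader might also infer that participants would be dosed with no current LVEF; the predose echo at onsite visits speaks against that. What is missing is an assured stable interval, not an echo. Confidence is medium, because a rule may sit in redacted text.

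**What to change.** In 5.1.2.2, anchor the no-adjustment interval to Day 1B and keep the sponsor's own interval length. This also covers a change made after a separate Screening B visit.

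Alternatively, state in 5.1.2.1 and in 6.1 (Part B) that EOS-A may serve as Screening only if no background HCM therapy was started or increased after EOS-A, and that otherwise the existing separate Screening B visit is used after the change. This would also make explicit what the resume option already implies.

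If redacted text already holds such a rule, a cross-reference in 5.1.2.2 is enough.

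The drafting cost is one changed anchor or one added sentence. For the few participants affected, the second option costs one already-defined visit. The first costs a delay to Day 1B of max(0, c + W − D) days: 0 to 14 at W = 14 and D = 28, with a maximum of 7 to 28 over the assumed range of W. They stay off MYK-224 during the delay.

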5.1.2.3 Washout and End of Study (Part B)

All participants will have a [REDACTED] washout period following the final dose of MYK-224. Participants will have an EOS-B clinic visit after the washout period is complete (at least [REDACTED] after the final dose of MYK-224). See [Table 2-3](#) for a list of assessments performed at these clinic visits.

Participants who discontinue MYK-224 dosing prior to EOT-B (see [Section 8.1](#)) will be asked to complete the washout and end-of-study assessments, if possible. Participants who discontinue from the study (eg, withdraw consent; see [Section 8.2](#)) will be asked to complete an Early Termination (ET-B) visit.

5.1.3 Data Monitoring Committee and Other Committees

5.1.3.1 Data Monitoring Committee

A Data Monitoring Committee will not be used in the study.

5.1.3.2 Executive Committee

The Executive Committee will plan an active role in providing scientific guidance and advice to the sponsor related to the design, conduct, results analysis, and publication strategy for this study. The committee will be composed of a subset of study investigators who are experts in cardiovascular disease, including HCM, with relevant clinical and methodological expertise. Meeting frequency, membership, and specific responsibilities will be further described in the Executive Committee charter.

5.2 Number of Participants

The total number of participants enrolled in this study is approximately [REDACTED]. The sample size is based on practical considerations and previous experience with similar studies (see details in [Section 10](#) Statistical Considerations). Participants who withdraw from the study or are discontinued for non-safety reasons may be replaced at the discretion of the Sponsor and PI.

Approximately [REDACTED] participants with symptomatic oHCM will be enrolled into each cohort. Each cohort has two subgroups:

- Cohort 1: MYK-224 monotherapy or MYK-224 with SOC using beta-blockers

- Cohort 2: MYK-224 with SOC using nondihydropyridine calcium channel-blockers or MYK-224 with SOC using disopyramide (combined with either a beta-blocker or a calcium channel-blocker)

The minimum size for each subgroup is [REDACTED]. The remaining [REDACTED] participants in each cohort can be enrolled into either subgroup within that cohort.

5.3 End of Study Definition

The start of the trial is defined as the first participant first visit.

End of trial is defined as the last participant last visit or scheduled procedure as shown as in the Schedule of Activities.

Study completion is defined as the final date on which data for the primary endpoint were or are expected to be collected, if this is not the same.

A participant is considered to have completed the study if he/she has completed the last procedure shown in the Schedule of Activities. Participants who complete all visits for Part A but do not participate in Part B will still be considered to have completed the study.

5.4 Scientific Rationale for Study Design

This study will be conducted in adult participants with symptomatic oHCM. The study will be open-label, and all participants will receive MYK-224. The purpose of this study is to characterize the safety, tolerability, efficacy, and exposure-response relationship of MYK-224 in participants with oHCM. The optional OLE will additionally [REDACTED] of MYK-224.

Because individual patients may require higher or lower exposures to MYK-224 to achieve clinically relevant improvement in LVOT obstruction, Part A of this study will follow an individualized dose-titration strategy that is guided by clinical response. The study will use intra-participant dose titration to identify the individual target dose and assess the pharmacological effects of that dose at steady state. The initial dose selection and titration levels are based on pre-clinical data as well as data from the FIH trial in healthy volunteers (MYK-224-001). [REDACTED]

See [REDACTED] Section 5.5 for details on dose justification in this study.

Dose titration in this study (Part A) will be based on [REDACTED]. Specifically, [REDACTED] (Section 2). The core laboratory TTE data collected 3 weeks (at least 21 days) following the initiation of each dose will be used to determine dose titration, which if indicated, will occur the following week (4 weeks post-initiation).

In each participant, dose escalation will proceed [REDACTED] until both [REDACTED]. Dose reductions may occur [REDACTED]. The individual target dose for this study is defined as the highest dose where these conditions are met (see [Section 7.4](#)).

Participants will enter the stable dosing period and continue to dose at their individual target dose for a minimum of 6 weeks (at least 42 days) of treatment with their target dose (or the maximum allowable dose), for a total treatment period of at least 12 weeks (at least 84 days). Transthoracic echocardiogram, PK samples, and safety labs will be collected [REDACTED] during the stable dosing period. This will provide sufficient time to evaluate the safety and efficacy of MYK-224 [REDACTED] for the highest tolerated dose in each participant. [REDACTED].

The objective of the study is to evaluate the safety, tolerability, and efficacy of MYK-224 alone and in combination with SOC therapies for HCM. The cohorts are staggered so that data from ongoing studies may be evaluated prior to initiating Cohort 2 to allow for modification of the starting dose or dose titration schedule if necessary. Cohort 2 includes participants with SOC consisting of either a nondihydropyrimidine calcium channel-blocker (verapamil or diltiazem) or dihydropyrimidine in combination with a beta-blocker or nondihydropyrimidine calcium channel-blocker. Both verapamil and diltiazem are moderate inhibitors of CYP3A4.

The initiation of Cohort 2 will be at the discretion of the Sponsor and will be informed by data obtained from Cohort 1, as well as from 2 on-going studies: 1) CV029005, a DDI study evaluating the effect of co-administration of MYK-224 and moderate (verapamil) and strong (itraconazole) [REDACTED] in healthy participants; 2) MYK-461-017 (VALOR-HCM), a clinical study evaluating mavacamten (a similar cardiac myosin inhibitor) in participants with oHCM who are eligible for septal reduction therapy, which includes the [REDACTED]. Cohort 2 will only be initiated once 50% of Cohort 1 participants have reached their target dose and the data from the CV029005 and VALOR-HCM study are available. The same dosing regimen as Cohort 1 will be used for Cohort 2 unless data from Cohort 1 and the indicated studies supports a change to this schedule.

Participants who successfully complete Part A will have the option to continue the study drug as a participant in Part B, a 2-year OLE study. In Part B, participants will start at the dose of MYK-224 on which they completed Part A with the exception of those who have had a change in background HCM therapy. In instances where participants have had adjustments in background HCM therapy following their completion of Part A, they may either resume the background therapy upon which they completed Part A at least [REDACTED] prior to screening for Part B or start Part B at a 5-mg dose (see [Section 7.4](#)). After the initial [REDACTED] of Part B, clinic visits will occur every [REDACTED] and will include clinical evaluation of symptoms, AE/SAE assessment, ECGs, TTEs, PK sampling, [REDACTED], and laboratory assessments. Dose modifications during Part B will be guided by local site-read TTEs (See [Section 7.4.2](#) for details).

Part B is designed to generate long-term data in participants with oHCM, using an approach that conforms to established ethical standards of safe human experimentation and the requirements of Good Clinical Practice (GCP).

